A RANDOMIZED CONTROLLED TRIAL OF SYMPTOM SCREENING BY CHILDREN WITH CANCER AND FEEDBACK TO PROVIDERS

BACKGROUND

There are approximately 1,500 children and adolescents diagnosed with cancer each year in Canada and there are currently over 10,000 children living with cancer nationally. Over the last few decades, impressive gains in survival have been made and now, more than 82% of children with cancer will be cured. These survival gains have been, in part, attributable to the provision of intensive therapies. However, as a result, most children suffer and experience severe and distressing treatment-related symptoms such as pain, fatigue and nausea. In our recent cross-sectional study of 302 inpatients 8-18 years of age, 99% of children experienced at least one bothersome symptom and 60% experienced at least one severely bothersome symptom, including severe pain in 22% and severe fatigue in 33% when asked about yesterday or today. Symptoms impact on quality of life (QoL), morbidity and future psychosocial functioning.

We know from studies in adult cancer patients that routine collection of patient-reported outcomes (PROs), improves patient-clinician communication,⁶ reduces distress⁷ and improves QoL.^{8,9} Furthermore, a recent randomized trial showed that routine PRO assessment may improve survival in adults with metastatic solid tumors.¹⁰ Thus, the routine measurement of PROs is considered essential to high quality of care.⁸ Challenges to the incorporation of PROs into clinical practice include lack of integration into clinical care work flow.¹¹ We also know that delivery of care consistent with evidence-based clinical practice guidelines (CPGs) can improve patient outcomes.¹² However, compliance with CPGs is generally poor.^{13,14}

Consequently, in Canadian adult oncology practice, screening and assessment of symptoms and improving accessibility of supportive care CPGs are important priorities. 15-18 Efforts by Cancer Care Ontario have culminated in the wide-spread use of a symptom screening tool based upon the Edmonton Symptom Assessment Scale (ESAS). 19 The ESAS is a validated tool which asks adult patients to rate the severity of nine common symptoms including pain, anxiety and nausea. In a satisfaction survey of 2,921 patients, 87% of respondents thought the ESAS was an important tool for letting healthcare providers know how they feel.²⁰ Furthermore, through an initiative with Cancer Care Ontario and the Canadian Partnership against Cancer, evidence-based guidelines were developed to manage severe symptoms identified by the tool.²⁰ These efforts have continued to evolve and led to the development and implementation of the Interactive Symptom Assessment and Collection (ISAAC) tool, Your Symptoms Matter, which allows patients to assess and monitor their symptoms through an online computer program. Your Symptoms Matter is available at kiosks in 14 regional cancer centers and 28 hospitals across Ontario. More than 27,000 patients are screened every month through the system. Implementation of ISAAC in the adult cancer setting improved health outcomes, 19 led to decreased emergency room visits and triggered clinical action for those with higher symptom scores.^{21,22} In contrast to these advances in adult cancer care, efforts in children are limited.²³ We used the Knowledge-to-Action cycle²⁴ as the conceptual framework to guide this research program.

Objectives

Among children and adolescents 8-18 years of age with cancer seen in hospital daily for 5 days, to determine if daily symptom screening and provision of symptom reports to healthcare providers with links to supportive care CPGs is associated with the following when compared to standard of care:

Aim 1: Better self-reported total SSPedi scores

Aim 2: Better self-reported individual SSPedi symptom, pain (Faces Pain Scale-Revised) and QoL (PedsQL 3.0 Acute Cancer Module) scores

Aim 3: Improved provider documentation of symptoms and intervention provision for symptom control We hypothesize that daily symptom screening and feedback with links to CPGs will be associated with lower total SSPedi scores (less bothersome symptoms), improvement in specific symptoms, pain and QoL and better documentation of symptoms and provision of interventions for symptom

Page 1 of 13

Preliminary Data

Version Date: 3Nov2023

Efforts in children to achieve routine symptom screening and enhance CPG compliance are limited.²³ We conducted a systematic review and identified the lack of appropriate symptom screening tools for children with cancer and that no study altered patient management based upon identified symptoms.²⁵

SSPedi: Early in our program, we recognized the lack of an appropriate symptom screening tool for pediatric cancer patients and thus, developed the Symptom Screening in Pediatrics Tool (SSPedi) (Figure 1).^{26,27} It is a 15-item symptom screening tool for children receiving cancer treatments; recall period is yesterday or today. Items were generated using a nominal group technique among pediatric cancer clinicians and a patient advocate.²⁸ Next, based upon input from 50 children receiving cancer treatments and 20 parents of pediatric oncology patients, we refined the paper and electronic versions of SSPedi and confirmed content validity, understandability and ease of use.²⁸⁻³⁰ The electronic version of SSPedi has an audio feature which allows specific questions or the

SSPedi: Symptom Screening in Pediatrics Please tell us how much each of these things bothered you yesterday circle that best describes the amount it bothered you: A little Medium A lot Feeling disappointed or sad 0 (3) Peeling scared or worried 0 0 0 0 0 0 0 0 0

0

0

0

0

0

0

0

0

0

0

0

0

0

0

0

0

0

0

0

0

0

0

Figure 1: SSPedi

SSPedi

(3)

entire instrument to be read aloud. A help feature provides synonyms for each symptom; these were derived primarily from children themselves during cognitive interviewing.

Constipation (hard to poop)

Next, we conducted a multi-center study to evaluate the psychometric properties of SSPedi. Among 502 children 8-18 years of age receiving cancer treatments, all were able to complete SSPedi without difficulty. We confirmed that SSPedi is reliable, valid and responsive to change. More specifically, the intraclass correlation coefficients were 0.88 (95% confidence interval (CI) 0.82 to 0.92) for test re-test reliability, and 0.76 (95% CI 0.71 to 0.80) for inter-rater reliability between children and parents. Mean difference in total SSPedi scores between groups hypothesized to be more and less symptomatic was 7.8 (95% CI 6.4 to 9.2; P<0.001). Construct validity was demonstrated as all hypothesized relationships among measures were observed. SSPedi was responsive to change; those who reported they were much better or worse on a global symptom change scale had significantly changed from their baseline score (absolute mean difference 5.6, 95% CI 3.8 to 7.5; P<0.001).

SPARK: Supportive care Prioritization, Assessment and Recommendations for Kids (SPARK) (Figure 2) is a web-based application which builds upon SSPedi and consists of two components: (1) a symptom screening component centered on SSPedi; and (2) a supportive care CPG component. CPGs contained within SPARK are those that meet rigorous development criteria established by the National Guideline Clearinghouse.³¹ There are patient, family and healthcare provider portals in SPARK. This proposal focuses on the patient and provider portals of SPARK.

SPARK pages and function were developed and iteratively refined by performing cognitive

interviews using the think aloud technique with 90 children receiving cancer

treatment and 60 healthcare providers until the website was considered satisfactory for longitudinal evaluation.

Next, in a pilot study conducted in preparation for the proposed RCT, we evaluated the feasibility of daily completion of SSPedi for 5 days among children who were either admitted to hospital or seen in clinic for 5 consecutive days. We defined feasibility as the completion of SSPedi within SPARK for at least 60% of on-study days in at least 75% of participants. In 3 months, we enrolled 20 participants of whom 18 completed assessments all 5 days. Two children missed one day each: one because of transfer to the intensive

Figure 2: SPARK

care unit due to a seizure and the second because she was seen in clinic only for blood work and was missed by the research team. Consequently, 100% of children met our *a priori* defined threshold for feasibility. All found completion of SSPedi via SPARK was easy and that SPARK was easy to navigate. They all thought daily completion was "about right" and not "too much" or "too little" for this population. All completely understood their own SPARK bar and line graphs.

Symptom Documentation and Interventions for Symptom Control: Our previous work included the description of symptoms documented in the health record and identification of intervention provision for symptoms. We created a standard operating procedure and a list of synonyms which met criteria for documentation of symptoms. For example "tired", "feel weak", "low energy" and "sluggish" were all both considered adequate documentation for fatigue. We also created a list of interventions for each symptom. For example, acetaminophen, ibuprofen and opioids were all considered interventions for pain. We reviewed the medical records of 100 consecutive children and adolescents who had completed symptom screening using SSPedi at The Hospital for Sick Children (SickKids). Symptom documentation and interventions were generally low for all symptoms except for pain and nausea and vomiting. Among those who reported at least medium bother, the proportion of patients in whom the symptom was documented by healthcare providers were: problems thinking or remembering (0%), changes in how body or face look (4%), changes in taste (3%), feeling more or less hungry (7%), tingly or numb hand or feet (10%) and cranky or angry (10%). Among the 21 children with moderately bothersome mouth sores, only 62% had any documentation and only 62% had provision of any intervention. Among the 33 with severely bothersome fatigue, only 18% had documentation and none were given an intervention. While pain was well documented (94%) and associated with interventions (100%), it was not completely controlled as 16% of children experienced severely bothersome pain despite intervention.

Factors Associated with Total Symptom Score: In our SSPedi validation study, among the 302 patients admitted to hospital and expected to be in hospital or clinic 3 days later, older age (P=0.0003) and stem cell transplant (P=0.030) were significantly associated with higher SSPedi scores in multiple regression.³²

Rationale

In order to improve symptom control in pediatric cancer, we need a feasible mechanism by which children with cancer can be enabled to report and track symptoms, for this information to be readily available to clinicians and to facilitate clinician access to supportive care CPGs for symptom management. This application builds upon our expertise in pediatric cancer symptom screening, CPG

[figure not shown]
Page 3 of 13

SPARK RCT Protocol

development and conduct of large multi-center pediatric cancer supportive care trials to improve pediatric cancer care and QoL. We anticipate the results to be directly translated into patient care if successful.

METHODS

This is a multi-center open label RCT and the study schema is shown as Figure 3. The setting is 8 Canadian academic institutions which care for children with cancer; all participated in our SSPedi validation study.⁴

Intervention and Control Groups

Intervention Arm: For those randomized to the intervention arm, we will use the procedures that were feasible in our longitudinal pilot study. Participants will complete symptom screening using SPARK once daily on a study-supplied iPad. For inpatients, daily reminders to complete SSPedi will appear on the iPad. Reports will be available to the child at any time. For outpatients, clinical research associates will provide the iPad in person daily and reports may be viewed at those encounters. Once daily was considered the optimal frequency for this population in our pilot study. The intervention is daily symptom screening with provision of reports to the healthcare team. Severe symptoms will result in email alerts. More specifically, SSPedi reports will be printed daily and provided in the patient chart or electronic health records (Figures 4a and 4b show example reports). On days 1 and 3, an alert will be emailed to the physician providing direct medical care if any symptom is "a lot" or "extremely" bothersome (score 3 or 4 on 0-4 scale). Reports and alerts will have links to SPARK-housed CPGs. The procedures developed for email correspondence have been approved by SickKids privacy consultants.

Page 4 of 13

[figure not shown]
[figure not shown]

Figure 4b: Provider Multi-Day Report

Control Arm: Participants randomized to the control arm will not complete daily symptom screening. They will complete SSPedi on days 1 and 5 to obtain the primary outcome. Health care providers will not be notified of their SSPedi scores and no symptom reports or symptom alerts will be generated.

For both study groups participant's guardian will be asked to fill out a household demographic form.

Allocating Participants

The allocation sequence will be computer generated and will be concealed from all participants, healthcare providers and research team members. Consenting participants will be randomized 1:1 to intervention vs. control groups using permuted block sizes and stratified by treatment (stem cell transplant yes vs. no) and age (8-10, 11-14 and 15-18 years) as our previous data suggested that these factors were the most strongly associated with higher total SSPedi scores. Assignment of enrolled participants will be communicated by email to the institutional principal investigator and clinical research associate following randomization.

Protecting against Bias

We hypothesize that the key elements to improving symptom control will be: (1) the systematic measurement of bothersome symptoms; (2) providing this information to healthcare providers; and (3) improving access to supportive care CPGs for providers. Given that this trial is randomized at the individual level and not at the cluster level, clinicians caring for patients in the control group may be more aware of supportive care CPGs. Although this information does represent contamination, we hypothesize that without a mechanism for children and adolescents to report symptoms, this level of contamination will not substantially influence the effectiveness of the intervention. However, we will measure documentation of symptoms and provision of interventions to facilitate interpretation of trial

results. We are not conducting a cluster randomized trial because there are only 17 centers in Canada that treat children with cancer, and site numbers and logistical challenges preclude this study design.

Since the main outcomes are subjective, they will be reported by the participants themselves. They will not be blinded to allocation, thus raising concerns of reporter bias. Participants in the intervention arm will not know which of the five SSPedi scores they provide for the trial is the outcome; this should lessen the concern about reporter bias. The use of a standard of care control arm, in contrast to an attention control arm, is consistent with the more pragmatic nature of this randomized trial.

In our control group, we will obtain SSPedi scores at baseline and day 5 as they are required for the planned statistical analysis. We will not share these scores with the child, family or providers and thus, we do not anticipate bias. Further, in our studies of SSPedi and SPARK, we explicitly asked children whether they shared scores with their providers and even when patients can access their reports at any time (which will not be the case in our control patients), they almost never tell their providers this information. Thus, the risk of contamination is minimal.

Planned Inclusion and Exclusion Criteria

We will include pediatric patients with cancer who are 8-18 years of age, who can understand English and who are expected to be in hospital or in clinic daily for 5 days. Five days was chosen to allow longitudinal daily evaluation but preserve feasibility as few children are admitted or seen daily for longer than 5 days. Exclusion criteria will be illness severity, cognitive disability, or visual impairment that preclude utilization of SPARK according to the primary healthcare team.

Study Duration

The study period is 5 days. The study is complete on day 5 after completion of the intervention and ascertainment of outcomes.

Primary and Secondary Outcome Measures

For both intervention and control groups, all outcomes will be obtained in an identical fashion. Primary and secondary outcomes will be obtained at baseline and day 5; a clinical research associate will visit the participant at those two visits to facilitate self-reported outcomes. The primary outcome will be the self-reported total SSPedi score on day 5. The total SSPedi score is a validated measure that reflects the total burden of bothersome symptoms experienced.⁴ The total score is the sum of each of the 15 items' Likert scores which range from 0 (not at all bothered) to 4 (extremely bothered) to yield a total score that ranges from 0 (no bothersome symptoms) to 60 (worst bothersome symptoms).

Secondary outcomes will be self-reported individual SSPedi symptom, pain (Faces Pain Scale-Revised) and QoL (PedsQL 3.0 Acute Cancer Module) scores. We will also measure documentation of symptoms and intervention provision for symptom control. Self-reported pain will be assessed using the Faces Pain Scale-Revised which consists of a series of horizontal faces that depict a neutral facial expression of no pain on the left and worst pain on the right. It has 6 faces and may be scored on a 0 to 10 scale in which higher numbers denote more pain. Faces Pain Scale-Revised is psychometrically sound and feasible for children 4 to 18 years of age. Self-reported QoL will be measured using the PedsQL 3.0 Acute Cancer Module. This measure is a multidimensional instrument that is reliable and valid in children with cancer. Si-38 It assesses pain and hurt, nausea, procedural anxiety, treatment anxiety, worry, cognitive problems, perceived physical appearance and communication. The self-report 7-day recall version will be used.

Documentation of symptoms and intervention provision for symptom control will be abstracted from the patients' health records using the procedures we developed. Interventions for each symptom will be categorized as any intervention provided vs. no intervention provided. Both documentation of symptoms and interventions for these symptoms will be described for each specific symptom. These outcomes will be obtained on day 5 with a one day window before and after the day 5 assessment. In other words, if the participant completed SSPedi on a Tuesday, we would accept documentation of that

Page 6 of 13

symptom (or provision of an intervention for that symptom) if it were recorded in the health records on Monday, Tuesday or Wednesday.

The primary and secondary PROs will be measured by patient self-report while documentation of symptoms and intervention provision will be abstracted from the health record. Self-reported PROs and QoL measures are essential in this study as the intervention is focused on reducing symptom burden.

Sample Size Justification

We used data from our SSPedi validation study for power calculations.⁴ We recruited 302 children who were hospitalized and expected to be in hospital or in clinic 3 days later. Children completed SSPedi on days 1 and 4 and a 5-point global symptom change scale on day 4. The average absolute change in total SSPedi scores for those who rated they were a little worse or a little better (1-point change) was 2.7 which is the minimally clinically important difference. The average standard deviation of the two total SSPedi scores (on days 1 and 4) was 8.5. Thus, with 80% power and alpha of 0.05, we will require 157 patients per group or 314 patients total. Assuming 10% will be non-evaluable, we will recruit 345 total.

Recruitment

All 8 participating institutions enrolled patients in our previous SSPedi validation study; all have experience with SSPedi, recruited patients in a timely fashion and submitted high quality data. Investigator calls twice a month will focus on recruitment status and enrollment issues. Specific outreach to each institutional principle investigator and clinical research associate will be made in the event of lagging accrual and a specific plan to rectify accrual will be made. If accrual continues to lag, the institution may be replaced.

Table 1 shows the number of expected eligible participants at the 8 sites; estimates were based on our pilot study. We anticipate 160 eligible patients per year. Thus, assuming that at least 60% of patients are identified and consent, we will complete enrollment within 4 years although accrual may take longer given the COVID-19 pandemic. Data analysis and knowledge dissemination will occur in year 5.

Table 1: Site (PI): Number new cancer	Year 1	Year 2	Year 3	Year 4	Year 5
patients annually (all ages)	Enroll	Enroll	Enroll	Enroll	
Toronto ([name]): 300-350	80	80	80	80	Analyze
Vancouver ([name]): 120-160	30	30	30	30	
Winnipeg ([name]): 40-60	10	10	10	10	Publish
London ([name]): 55-70	10	10	10	10	
Hamilton ([name]): 65-80	10	10	10	10	KTE
Ottawa ([name]): 55-70	10	10	10	10	
Halifax ([name]): 55-70	10	10	10	10	
Edmonton ([name]) 40-70	10	10	10	10	
TOTAL	170	170	170	170	

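### Could the day-1 SSPedi, the baseline in the primary ANCOVA, be biased because the text does not place it before children learn their arm?

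*Combined protocol and SAP*

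**What the plan says.** **Order of events.** Under Allocating Participants, "Consenting participants will be randomized 1:1 to intervention vs. control groups using permuted block sizes". Then "Assignment of enrolled participants will be communicated by email to the institutional principal investigator and clinical research associate following randomization". That section also says the allocation sequence is concealed. Concealment protects the assignment, but it does not settle when the child hears the result.

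**Day-1 SSPedi.** For the control arm, "They will complete SSPedi on days 1 and 5 to obtain the primary outcome". For the intervention arm, day 1 is one of five daily scores and can prompt a message to the physician: "On days 1 and 3, an alert will be emailed to the physician providing direct medical care", if any symptom scores 3 or 4. Primary and Secondary Outcome Measures adds: "Primary and secondary outcomes will be obtained at baseline and day 5; a clinical research associate will visit the participant at those two visits". It also says that outcomes are collected identically in the two arms. Comparative Analyses uses the baseline SSPedi score as a covariate in the primary ANCOVA.

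**Reporter bias.** Protecting against Bias says of the children: "They will not be blinded to allocation, thus raising concerns of reporter bias". The mitigation is "Participants in the intervention arm will not know which of the five SSPedi scores they provide for the trial is the outcome", and the protocol claims only that this should reduce the concern.

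**Sample size.** The target difference is 2.7 points. "The average standard deviation of the two total SSPedi scores (on days 1 and 4) was 8.5", and 157 children per group are required for 80% power at alpha 0.05.

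**The concern.** In the order of the readable text, consent leads to randomization, then to an email to the research associate, a role that also helps children with the baseline questionnaires. Day-1 SSPedi appears only in the two arm descriptions, as a task of children already assigned. A site could therefore take the baseline from a child who knows whether the care team will see the answers.

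If that knowledge moves day-1 reporting in one arm, the ANCOVA adjusts for a contaminated covariate and carries part of the shift into the treatment effect. The size and direction could not be recovered later, because no clean baseline would exist.

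The masking safeguard also looks thin. Control children give only two scores, so it cannot apply to them. In the intervention arm, the research-associate visit and the extra questionnaires mark out day 5, at least for inpatients.

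**Working it through.** **Inputs.** From Sample Size Justification: difference 2.7, SD 8.5, 157 per arm. Assumed, because the documents do not give them: the within-arm slope of day 5 on day 1 (0.6, range 0.5 to 0.7), and reporting shifts in the intervention arm relative to control, s1 on day 1 and s5 on day 5 (1 to 2 points). SDs are taken as equal on the two days, so the slope equals the correlation.

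**The plan's own figure.** n per arm = 2 × (1.960 + 0.842)² × (8.5/2.7)² = 155.6, so 156. The t-based calculation gives 156.5, so 157. The stated number reproduces as a two-sided test with no credit taken for baseline adjustment.

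**Bias in the ANCOVA effect.** Bias = s5 − slope × s1, where negative favours the intervention because lower SSPedi is better.

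**Standard error.** SE = 8.5 × √(1 − slope²) × √(2/157). At slope 0.6 this is 8.5 × 0.8 × 0.1129 = 0.767. With no shift, power for a true 2.7-point benefit is Φ(2.7/0.767 − 1.960) = 94%.

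**Shift on day 1 only (s5 = 0), slope 0.6.**
- s1 = 1: bias −0.6, two-sided type I error 12%.
- s1 = 2: bias −1.2, type I error 35%.
- Over slopes 0.5 to 0.7 and shifts of 1 to 2 points: bias 0.5 to 1.4 points in favour of the intervention, type I error 9% to 53%.

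Here, taking the baseline before disclosure removes the bias entirely.

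**Same shift on both days, slope 0.6.** Taking the baseline before disclosure sets s1 to 0 and leaves s5 in full.

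| Shift on both days | Bias, baseline after disclosure | Bias, baseline before disclosure | Consequence of moving the baseline |
|---|---|---|---|
| +1 | 1 − 0.6 = +0.4 | +1.0 | power 85% to 60% |
| +2 | 2 − 1.2 = +0.8 | +2.0 | power 70% to 15% |
| −1 | −1 + 0.6 = −0.4 | −1.0 | type I error 8% to 26% |

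The loss of power from 94% to 85% or 70% in this scenario comes from the day-5 shift. The baseline term offsets part of it, and removing that term multiplies the net bias by 1/(1 − 0.6) = 2.5.

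**Break-even.** For shifts of the same sign, moving the baseline reduces the net bias only if slope × s1 > 2 × s5. At slope 0.6 that means s1 > 3.3 × s5. It also helps if the two shifts have opposite signs. No passage suggests that arm knowledge acts mainly on day 1.

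**Dropping the baseline covariate.** SE = 8.5 × √(2/157) = 0.96, power 80%. This too removes only the slope × s1 term and leaves s5 whole.

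**Masking, by reading.** The statement names the intervention arm only, so it makes no claim about controls. It sits directly after the admission that children are unblinded. For outpatients a research associate brings the iPad every day (Intervention Arm), so the day-5 visit is a weak cue for them.

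**The case for a change.** The strongest case for acting is that the protocol itself concedes the mechanism, and that one sentence on order would cost almost nothing: no new visits, questionnaires or participants. A baseline taken before disclosure is sound general practice. It leaves a single reporting bias, s5, whose direction is easier to interpret than a difference of two unknown terms. Without it, no later analysis can recover a clean baseline, and a day-1-only shift of 2 points could raise type I error to about a third.

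Much of this stands. The readable text is silent on the order, the formulas are right, and writing the order down would be harmless as a clarification. Two parts do not carry through. First, silence in the readable text is not a stated rule that baseline follows disclosure. The assignment email goes to staff, nothing says the child is told before completing day-1 SSPedi, and the missing schema may show the sequence. Secondly, a baseline that is easier to interpret is not the same as a less biased treatment effect. Under a persistent shift the net error grows, and the day-5 reporter bias, which the protocol already admits, remains either way.

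**Conclusion.** The concern does not call for a change. What remains is an unstated detail of sequence that sites can settle sensibly and that Figure 3, not shown in our copy, may already give. It is not a rule shown to produce a wrong result.

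The size of any harm rests wholly on assumed slopes and shifts. At slope 0.6, a day-1-only shift of 1 to 2 points gives 0.6 to 1.2 points of bias, or 22% to 44% of the 2.7-point target (0.6/2.7 and 1.2/2.7). The same shift on both days gives 0.4 to 0.8 points, and taking the baseline before disclosure would raise that to 1.0 to 2.0. A gain from reordering is therefore not demonstrated.

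The masking statement is a matter of degree. It is confined to the intervention arm, claims only to lessen the problem, and stands beside an explicit acknowledgement of reporter bias. Rewording it would alter no result. Self-report without blinding is an accepted limitation of this pragmatic design and belongs in the interpretation of the trial.
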